Since the EnvoyGram IT levels are calibrated to each patient, the "predicted" EnvoyGram IT thresholds are equal to the baseline pre-implant unaided audiogram for each test frequency. For instance, a patient with 55 dB baseline air conduction threshold at 1 kHz and 80 nm measured IC would have a predicted EnvoyGram IT of 58 dB at 1 kHz (first level above baseline unaided threshold of 55 dB).

Bone Conduction/Safety Algorithm

Safety Algorithm Explanation:

The first level of the safety algorithm will use standard bone conduction (BC) thresholds. Bone conduction thresholds are measured in the implanted ear at 0.5, 1.0, 2.0, and 4.0 kHz at baseline and follow-up visits. If less than two (2) of the follow-up thresholds are more than 10 dB greater than the baseline thresholds, then the individual test frequencies are evaluated. At each test frequency, if the follow-up threshold is less than 20 dB greater than the baseline threshold then the algorithm is considered complete, with a conclusion that no change cochlear function occurred. However, if at least two (2) of the thresholds have increased more than 10 dB or if any individual threshold has increased by 20 dB or more, then the EnvoyGram data is evaluated.

The second level of the safety algorithm will use EnvoyGram thresholds. Baseline unaided air conduction pure tone thresholds at 0.5, 1.0, 2.0, and 4.0 kHz are measured at baseline. Similarly, EnvoyGram thresholds are measured in the implanted ear at 0.5, 1.0, 2.0, and 4.0 kHz at follow-up visits. Based on the intra-operative intact chain data, an EnvoyGram equivalent dB threshold is calculated for each of the four test frequencies. If less than two (2) of the follow-up EnvoyGram thresholds are more than 10 dB greater than the baseline thresholds, then the individual test frequencies are evaluated. At each test frequency, if the follow-up EnvoyGram threshold is less than 20 dB greater than the baseline threshold

then the algorithm is considered complete, with a conclusion that no change in cochlear function occurred. However, if at least two (2) of the EnvoyGram thresholds have increased more than 10 dB or if any individual EnvoyGram threshold has increased by 20 dB or more, then the algorithm is considered complete with a conclusion that a change in cochlear function occurred.

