For patients with moderate to severe sensorineural hearing loss, non-responses (NR) are not uncommon during bone-conduction testing. If an NR occurs during baseline bone conduction testing, that test frequency is not evaluated (for the same patient) in the follow-up bone conduction portion of the safety algorithm. However, if an NR occurs during follow-up bone conduction testing (and is not preceded by a baseline NR at the same test frequency), the corresponding EnvoyGram threshold is substituted at the bone conduction NR test frequency.

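### A new bone-conduction non-response is replaced by an air-referenced EnvoyGram value with no stated baseline, so level 1 can close an ear that level 2 would call changed

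*Combined protocol and SAP*

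**What the plan says.** Section 5.2 assigns primary Objective 5 (cochlear function unchanged) to the Safety Algorithm. It cites Attachment C, but the algorithm is printed as Attachment A. No other procedure is given for this objective.

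The algorithm has two levels, each using 0.5, 1, 2 and 4 kHz.

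- **Level 1.** "The first level of the safety algorithm will use standard bone conduction (BC) thresholds" at baseline and follow-up. "If less than two (2) of the follow-up thresholds are more than 10 dB greater than the baseline thresholds", and no single threshold has risen by 20 dB or more, "then the algorithm is considered complete, with a conclusion that no change cochlear function occurred". Only ears that fail this step go on to level 2.
- **Level 2.** The follow-up measure is the EnvoyGram, and its baseline is air conduction: "Baseline unaided air conduction pure tone thresholds at 0.5, 1.0, 2.0, and 4.0 kHz are measured at baseline". The ear is called changed "if at least two (2) of the EnvoyGram thresholds have increased more than 10 dB or if any individual EnvoyGram threshold has increased"; for the single-frequency part the limit is a rise of at least 20 dB.

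The section on the EnvoyGram IT ties the measure to air conduction: predicted "thresholds are equal to the baseline pre-implant unaided audiogram for each test frequency".

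The closing paragraph of Attachment A deals with BC non-responses (NR). A frequency with an NR at baseline is left out of level 1. If the follow-up NR "is not preceded by a baseline NR at the same test frequency", then "the corresponding EnvoyGram threshold is substituted at the bone conduction NR test frequency". Only the follow-up value is replaced. The paragraph does not say which baseline the substituted value is compared with.

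**The concern.** Level 1 names only one baseline, the BC threshold. An analyst who follows the text will therefore subtract baseline BC from an EnvoyGram value that is calibrated to baseline AC. The resulting shift includes the ear's baseline difference between forehead BC and AC, which is not a change over time. The inclusion criteria (4.1.1) define the loss by air conduction and set no numerical limit on that difference.

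The two possible errors have unequal consequences. If level 1 refers an ear wrongly, level 2 re-scores it against AC. If level 1 closes an ear wrongly, the EnvoyGram is never read at level 2. The substitution also acts only in ears whose BC response has newly disappeared at some frequency, and Attachment A describes non-responses as common enough in this population to need a rule.

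At stake are the cochlear-change classification reported for Objective 5 and the adverse-event count, because section 4.7.1 counts a failure of the algorithm as an adverse event.

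**Working it through.** **Plan's own figure.** Attachment A gives a predicted EnvoyGram of 58 dB for AC 55 dB and an 80 nm chain. On the 80 nm row of its level table (28, 34, 40, 46, 52, 58, …) the first level above 55 is 58, so the figure reproduces. The typical row (34, 40, 46, 52, 58, 64, 70, 76, …, 100) also gives 58. The examples below use the typical row. The text elsewhere gives ranges of 55 to 119 and 55 to 117 dB, which do not match the table; the table is used because it agrees with the 58 dB example.

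**Identity.** Let AC and BC be the baseline thresholds and EG the follow-up EnvoyGram at a frequency with a new NR.

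- Level 1, read literally: S1 = EG − BC
- Level 2: S2 = EG − AC
- Hence S1 = S2 − (BC − AC)

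If BC = AC, the mismatch has no effect. If BC is higher (poorer), S1 understates S2. If BC is lower (better), S1 overstates S2.

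**Example with two new NRs.** The ear values are illustrative; the limits and levels are the plan's. The other two frequencies are stable.

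| | Frequency 1 | Frequency 2 | Outcome |
|---|---|---|---|
| Baseline AC / BC | 55 / 60 | 55 / 60 | |
| Follow-up BC / EG | NR / 70 | NR / 70 | |
| Level 1 shift | 70 − 60 = 10 | 70 − 60 = 10 | neither exceeds 10: closed as unchanged |
| Level 2 shift, raw AC | 70 − 55 = 15 | 70 − 55 = 15 | two exceed 10: changed |
| Level 2 shift, predicted level 58 | 70 − 58 = 12 | 70 − 58 = 12 | two exceed 10: changed |

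A 5 dB excess of BC over AC reverses the result on either reading of the level 2 baseline.

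**One new NR.** With AC 55, BC 60 and EG 76, level 1 gives 76 − 60 = 16 and closes. Level 2 gives 76 − 55 = 21 (changed) against raw AC, but 76 − 58 = 18 (not changed) against the predicted level. This case therefore depends on a choice that the plan leaves open. With BC 65 and EG 82, level 1 gives 17 and level 2 gives 27 or 24, so the conflict holds on both readings.

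**Direction.** Take AC from 45 to 70 dB in 5 dB steps against the twelve typical levels. There are 26 combinations with EG − AC ≥ 20. Level 1 fails to flag at 20 dB:

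| BC − AC (dB) | −15 to 0 | +5 | +10 | +15 |
|---|---|---|---|---|
| Of 26, not flagged | 0 | 5 | 10 | 15 |

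These are counts of grid cells, against raw AC and for the single-frequency limit only. They show direction and are not rates in subjects.

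**Test of the obvious repair (score EG against AC within level 1).** At 2 kHz take AC 65, BC 60, new NR, EG 82. At 4 kHz take AC 60, BC 55 rising to 65, EG 76. The other frequencies are stable.

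- Current literal rule: 82 − 60 = 22 ≥ 20, so level 2 is read. It gives 82 − 65 = 17 and 76 − 60 = 16: changed.
- Re-scored within level 1: 82 − 65 = 17 at one frequency and 65 − 55 = 10 at the other. Only one exceeds 10 and none reaches 20: closed as unchanged.

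That repair can create the error it is meant to remove.

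**The case against.** The closing paragraph is silent on the reference, so the sponsor may have intended AC. Comparison with BC is the natural reading, because level 1 has no other baseline, but it is an inference. A stated reference is needed in either case, or two analysts could classify the same ear differently.

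Level 2 is not the truth. Attachment A makes forehead BC the primary test and puts the accuracy of the intact-chain measurement at about ±6 dB. A tiered design also closes some level-2-positive ears by construction. For example, with BC = AC = 55 at two frequencies, EG 70 at both, an NR at one and a BC rise of 10 at the other, level 1 sees 15 and 10 and closes, while level 2 would see 15 and 15. No reference mismatch is involved. This stands. The criticism is therefore limited to the level 1 result departing from the plan's own level 2 rule because of a baseline difference unrelated to change.

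The harmful direction needs baseline BC recorded poorer than AC, and the documents contain no AC–BC data. This also stands. Such ears are plausible, since the introduction to Attachment A accepts BC retest results outside ±10 dB, but their frequency is not known.

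A reader might infer that the rule misses a large share of damaged ears, or that it is biased towards no change across the study. The documents do not support this: any percentage would rest on an assumed systematic BC deficit. Nor can it be inferred that the Objective 5 conclusion would flip, because section 5.2 sets no hypothesis, margin or success criterion for that objective.

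**Conclusion.** The point holds as a defect in the rule as written. A new NR puts an AC-referenced value into a step whose only named baseline is BC, and the resulting shift is off by exactly the baseline BC − AC difference. Where BC is poorer than AC at that frequency, an ear that meets the level 2 change rule can be closed finally as unchanged; the two-frequency example shows this with a 5 dB difference on either reading of the level 2 baseline. Where BC is better, the mismatch produces extra referrals, which level 2 re-scores.

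The conclusion rests on the literal reading of level 1. The number of subjects affected is unknown, because the documents give neither AC–BC differences nor the number of new NRs. The effect is on individual cochlear-change classifications and the related adverse events, not on a formal test. The change should be made, since it is cheap and the uncorrected error is the reassuring one.

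**What to change.** Replace the last sentence of Attachment A with wording such as: *If bone conduction gives no response at follow-up at a frequency with a measurable baseline, level 1 counts as failed and the ear is assessed at level 2, where all EnvoyGram thresholds are scored against the level 2 air-conduction baseline.*

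In the level 2 paragraph, state whether that baseline is the raw AC threshold or the predicted EnvoyGram level (55 or 58 dB in the plan's own example), and reconcile the EnvoyGram ranges in the text with the level table.

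Do not simply re-score the substituted value against AC within level 1: as shown above, that can close ears which the current rule refers. Direct referral avoids this, and it also sends the one-NR tiered case to level 2.

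The cost is a sentence or two and a small change to the analysis code. Table 1 already schedules baseline air conduction and the EnvoyGram at activation and at every later visit, so no test or visit is added. The downside is that somewhat more ears are read at level 2 and a few more may be classified as changed.
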